## 11.4 Primary Objective

The primary objective is to estimate the change in VO2peak at after 12 weeks from baseline in treatment-naïve mRCC patients treated with sunitinib on schedules 4/2 and 2/1 separately.

### 11.4.1 Variable

The primary endpoint is the change in peak oxygen uptake ( $\Delta$ VO2peak) from week 1 to through week 12 in each group.

### 11.4.2 Statistical Hypothesis, Model, and Method of Analysis

The primary analysis will be checking if there is a significant change in peak oxygen uptake (VO2 peak) from baseline to through week 12 for each schedule, using a paired t-test. The primary analysis will be done for complete cases, (i.e., patients with VO2peak measured at baseline and after week 12) in the ITT population.

## 11.5 Secondary and Exploratory Objectives

For subjects with VO2 peak measures at week 4 or week 5, descriptive statistics including mean, standard deviation, minimum and maximum of VO2peak changes from baseline to week 4 and to week 5 will also be reported to assess early effects of each sunitinib schedule. Descriptive statistics for other secondary and exploratory endpoints will also be reported for each sunitinib schedule.

In addition, a random effects model will be used to assess the effect of different sunitinib schedules on the VO2 peak change. In the model repeated measurements of VO2 peak change at week 4, 5 and through week 12 from baseline are outcomes, schedule indicator (0 for schedule 4/2, 1 for schedule 2/1) is chosen as the main factor, baseline VO2 peak value and patient characteristics are other included covariates. Similarly, random effects models with other continuous repeated measures (i.e., resting and stress cardiac function and muscle strength) as dependent variables will also be used to analyze the schedule effects.

Sensitivity analyses will be performed for the primary endpoint and key secondary endpoint using Last Value Carried Forward (LOCF) methods. The intent of this sensitivity analysis is to assay the robustness of results observed in the modified ITT population.

Eligibility rate, acceptance rate and adverse event rate will be reported descriptively.

Eligibility rate is defined as the number of subjects eligible for the study divided by the number approached for the study (i.e., screen fail rate).

Acceptance rate is defined as the number of patients agreeing to participate divided by total number randomized.

Rates of adverse events, classified by CTCAE v4.0, will be displayed by body system and preferred term for each arm.

For analysis of the plasma angiome multiplex ELISA data, correlations among analytes will be evaluated by Spearman analysis. Analyte levels at baseline and changes on-treatment will be correlated with baseline VO2peak and changes in VO2peak, respectively.

Descriptive statistics and graphical reporting of group and individual patient data will be used to report changes in step counts and blood pressure over time (daily monitoring). We will also determine if there is any association between steps/day and measurements of VO2peak and association between steps/day and blood pressure measurements of VO2peak.

## 11.6 Sample Size Calculation

The primary purpose of this study is to check if changes in cardiopulmonary function (VO2peak) in patients from baseline to through week 12 is significant for each sunitinib schedules.

This is a pilot study in which 15 evaluable patients per arm will be randomized with equal probability to either the sunitinib 4/2 or 2/1 schedule. The estimated variance based on a previous pilot study is 3.2 ([name]; unpublished data).

Assuming 1) the same variance at baseline and 12 weeks, and 2) no correlation between the two VO2peak measurements at baseline and 12 weeks, based on 2-sided, paired t-test with 15 patients, the VO2peak mean difference of 2.0 ml kg min from baseline to after 12 weeks can be detected with 80% power and significance level 0.05. If we assume a correlation of 0.20 between the two VO2peak measurements, then the VO2peak mean difference of 1.8 ml kg min from baseline to after 12 weeks can be detected. **Note:** Because VO2peak typically declines by only about 1% per year in adults, this magnitude of decline is believed to be clinically significant.

Because 1) the primary endpoint is mean difference in VO2peak at after 12 weeks) 30 total patients are required for adequate evaluation, patients who are not able to undergo CPET for determination of VO2peak at after 12 weeks will be replaced. We estimate a 20% dropout rate so that 36 patients will need to be accrued in order to have 30 total evaluable patients (15 evaluable in each arm).

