### 5.3.3 Randomization

When the subject has been registered, has completed screening, and has been found eligible post-baseline testing, the study coordinator will request the subject's random assignment to one of the two treatment arms from the Medidata RAVE database.

For this pilot study, subjects will be randomly assigned (randomized) with equal probability to either sunitinib schedule 4/2 or 2/1. This study is open label, meaning that neither subjects nor study personnel will be blinded to treatment assignment.

**Note:** For subjects who are not eligible and fail the screening process, no further action is necessary and no additional information will be collected. However, the number of screen failures and reason for screen failure will be collected and tallied at the end of the study.

Case report forms will only be completed for those registered and randomized subjects, including those who do not receive treatment. However, subjects who do not receive the assigned treatment will be replaced and not counted toward the overall study sample size. Data limited to demographics and reason for screen failure will be collected for screen failures.

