### **5.6 Definition of Evaluable Subjects**

For the primary analysis of change in VO2peak, patients with measurements at baseline and after 12 weeks are evaluable.

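### Accruing 36 patients at the stated 20% dropout gives 28.8 evaluable, not 30; the three figures in Section 11.6 need 38 accrued to agree

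*Combined protocol and SAP*

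**What the plan says.** Section 11.6 sets the design at 15 evaluable patients per arm: "This is a pilot study in which 15 evaluable patients per arm will be randomized". Its power statement is for a two-sided paired t-test with 15 patients at the 0.05 level. It claims 80% power for a mean VO2peak change of 2.0 ml/kg/min with no correlation between the two measurements, or 1.8 with a correlation of 0.20.

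The section then moves to accrual: "We estimate a 20% dropout rate so that 36 patients will need to be accrued in order to have 30 total evaluable patients", and specifies 15 evaluable in each arm. Section 5.6 defines the term: "patients with measurements at baseline and after 12 weeks are evaluable". Section 5.3.3 allocates patients to the two schedules with equal probability.

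Three places deal with replacement:

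- **Section 11.6** replaces "patients who are not able to undergo CPET for determination of" VO2peak after 12 weeks.
- **Section 8.8.3** replaces only those who withdraw before the baseline assessment of the primary endpoint is complete.
- **Section 5.3.3** replaces patients who do not receive their assigned treatment and leaves them out of the sample size.

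**The concern.** A dropout rate applies to the patients who enter, so the number to accrue is the evaluable target divided by the proportion retained. The stated 36 is what results from adding 20% of the target to the target. That understates the requirement, because the added patients are also subject to dropout.

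The primary analysis is a separate paired t-test in each arm on complete cases (Sections 11.1 and 11.4.2), so each arm needs its own 15. The margin is thin: 15 per arm just clears 80% power for 2.0, and one patient fewer does not. Either the trial stops at 36 and expects to fall short of its evaluable target, or it replaces losses until it has 30 and should expect to pass the accrual figure given in the protocol.

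**Working it through.** **Inputs.** From Section 11.6: dropout 20%; stated accrual 36; target 30 evaluable (15 per arm); variance 3.2 at each time; correlation 0 or 0.20; two-sided paired t-test at 0.05. From Section 5.3.3: equal allocation, taken here as an exact 1:1 split.

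**Reproducing the plan's figure.** Target × (1 + dropout) = 30 × 1.20 = 36, and per arm 15 × 1.20 = 18. This matches exactly. The plan shows no formula, so this is an inference about how 36 was reached.

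**What 36 delivers.** Accrual × (1 − dropout) = 36 × 0.80 = 28.8, and per arm 18 × 0.80 = 14.4.

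**What the target needs.** Target / (1 − dropout) = 30 / 0.80 = 37.5, so 38. Per arm, 15 / 0.80 = 18.75, so 19. Check: 38 × 0.80 = 30.4, or 15.2 per arm.

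**Dropout at which 36 is right.** (36 − 30) / 36 = 6 / 36 = 16.7%.

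**Chance of reaching the target if accrual is fixed and nobody is replaced.** Binomial, with each patient evaluable with probability 0.80 independently:

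| Accrued | Expected evaluable | P(at least 30 in total) | P(at least 15 in both arms) |
|---|---|---|---|
| 36 (18 + 18) | 28.8 | 0.40 | 0.25 |
| 38 (19 + 19) | 30.4 | 0.66 | 0.45 |

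**Expected accrual if losses are replaced until 30 are evaluable.** 30 + 6 + 1.2 + … = 30 / (1 − 0.20) = 37.5. More than 36 must be accrued whenever the first 36 yield fewer than 30, which has probability 1 − 0.40 = 0.60.

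**Effect on power.** The variance of the change is 2 × 3.2 × (1 − correlation): 6.4 (SD 2.53) at correlation 0, and 5.12 (SD 2.26) at 0.20. Power comes from the noncentral t distribution with n − 1 degrees of freedom and noncentrality difference × √n / SD.

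| n per arm | Power for 2.0, correlation 0 | Detectable at 80% power | Power for 1.8, correlation 0.20 | Detectable at 80% power |
|---|---|---|---|---|
| 15 | 0.81 | 1.97 | 0.82 | 1.76 |
| 14 | 0.78 | 2.05 | 0.79 | 1.83 |

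The n = 15 row reproduces the protocol's 2.0 and 1.8. The power statement is therefore sound for 15 evaluable per arm; the fault is in the accrual step.

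**The case against.** The strongest reply is that replacement makes 36 a forecast rather than a cap. Section 11.6 says patients who cannot have the 12-week test will be replaced because 30 are needed, and nothing in the protocol calls 36 a ceiling. On that reading 15 evaluable per arm is the design quantity, the power claim is protected, and the fixed-accrual probabilities above do not describe what would happen.

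The point about those probabilities stands: they apply only if accrual stops at 36. But replacement does not make 36 right. Replacements drop out too, so the forecast should be 37.5. The rule itself is also unsettled. If Section 8.8.3 governs, patients lost after baseline are not replaced and the expected 28.8 remains.

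A second reply is that the effect is negligible. At 14 per arm the detectable differences are about 2.05 and 1.83, close to the one-decimal figures in the protocol. Power drops about three points. The zero-correlation assumption is conservative if repeated VO2peak measurements are positively correlated, and this is a pilot meant to inform a later study. All of that is fair. It limits the consequence but does not make the three figures agree.

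Finally, 20% may have been intended as over-accrual relative to 30. The sentence would then be misworded rather than miscalculated, but it calls the figure a dropout rate and would still need changing.

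**Conclusion.** The accrual figure is wrong as written. At 20% dropout among those accrued, 36 patients give 28.8 evaluable, and 30 evaluable need 38. The shortfall is two patients overall and one per arm. Losing one evaluable patient per arm costs about three points of power and takes it just below the stated 80%.

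The accrual result needs only the three numbers in Section 11.6 and the ordinary meaning of a dropout rate. The power figures also rest on the protocol's variance of 3.2 and its two correlation assumptions. The probabilities of reaching the target also assume independent dropout, an exact 1:1 split and no replacement. With full replacement the evaluable number can be met, but planned accrual is then understated.

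**What to change.** Change one figure in Section 11.6 so that the three agree. Any of these would do:

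- accrue 38 (19 per arm) at 20% dropout for 30 evaluable;
- keep 36 and 30, and state and justify an assumed dropout of 16.7%;
- keep 36 and 20%, and state 28 to 29 evaluable with a detectable difference of about 2.05 (about 1.83 at correlation 0.20) for 14 per arm.

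In the same place, say whether replacements are counted within the accrual total or added to it, and reconcile the replacement rules in Sections 5.3.3, 8.8.3 and 11.6. Because 38 makes 30 evaluable the expectation and not a certainty (66% without replacement), the text should also say whether accrual may continue past the stated number.

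The cost is a sentence or two of text and either two more planned patients or a slightly less favourable stated assumption or detectable difference. The endpoint and the primary analysis do not change.

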# 12 ADMINISTRATIVE AND ETHICAL CONSIDERATIONS

## 12.1 Regulatory and Ethical Compliance

This protocol was designed and will be conducted and reported in accordance with the International Conference on Harmonization (ICH) Harmonized Tripartite Guidelines for Good Clinical Practice, the Declaration of Helsinki, and applicable federal, state, and local regulations.

## 12.2 DUHS Institutional Review Board and DCI Cancer Protocol Committee

The protocol, informed consent form, advertising material, and additional protocol-related documents must be submitted to the DUHS Institutional Review Board (IRB) and DCI Cancer Protocol Committee (CPC) for review. The study may be initiated only after the Principal Investigator has received written and dated approval from the CPC and IRB.

The Principal Investigator must submit and obtain approval from the IRB for all subsequent protocol amendments and changes to the informed consent form. The CPC should be informed about any protocol amendments that potentially affect research design or data analysis (i.e., amendments affecting subject population, inclusion/exclusion criteria, agent administration, statistical analysis, etc.).

The Principal Investigator must obtain protocol re-approval from the IRB within 1 year of the most recent IRB approval. The Principal Investigator must also obtain protocol re-approval from the CPC within 1 year of the most recent IRB approval, for as long as the protocol remains open to subject enrollment.

### **12.3 Informed Consent**

The informed consent form must be written in a manner that is understandable to the subject population. Prior to its use, the informed consent form must be approved by the IRB.

The Principal Investigator or authorized key personnel will discuss with the potential subject the purpose of the research, methods, potential risks and benefits, subject concerns, and other study-related matters. This discussion will occur in a location that ensures subject privacy and in a manner that minimizes the possibility of coercion. Appropriate accommodations will be made available for potential subjects who cannot read or understand English or are visually impaired. Potential subjects will have the opportunity to contact the Principal investigator or authorized key personnel with questions, and will be given as much time as needed to make an informed decision about participation in the study.

Before conducting any study-specific procedures, the Principal Investigator must obtain written informed consent from the subject or a legally acceptable representative. The original informed consent form will be stored with the subject's study records, and a copy of the informed consent form will be provided to the subject.

### **12.4 Privacy, Confidentiality, and Data Storage**

The Principal Investigator will ensure that subject privacy and confidentiality of the subject's data will be maintained. Research Data Security Plans (RDSPs) will be approved by the appropriate Duke clinical research unit for the Duke site.

To protect privacy, every reasonable effort will be made to prevent undue access to subjects during the course of the study. Prospective participants will be consented in an exam room where it is just the research staff, the patient and his family, if desired. For all future visits, interactions with research staff (study doctor and study coordinators) regarding research activities will take place in a private exam room. All research related interactions with the participant will be conducted by qualified research staff who are directly involved in the conduct of the research study.

To protect confidentiality, subject files in paper format will be stored in secure cabinets under lock and key accessible only by the research staff. Electronic records of subject data will be maintained using a dedicated database which is housed in an encrypted and password-protected DCI file server. Access to electronic databases will be limited to delegated personnel. The security and viability of the IT infrastructure will be managed by the DCI and/or Duke Medicine.

Upon completion of the study, research records will be archived and handled per DUHS HRPP policy. Subject names or identifiers will not be used in reports, presentations at scientific meetings, or publications in scientific journals.

### **12.5 Data and Safety Monitoring**

Data and Safety Monitoring will be performed in accordance with the DCI Data and Safety Monitoring Plan. For a more detailed description of the DSMP for this protocol, refer to the DSMP document.

## **12.6 Protocol Amendments**

All protocol amendments must be initiated by the Principal Investigator and approved by the IRB prior to implementation. IRB approval is not required for protocol changes that occur to protect the safety of a subject from an immediate hazard. However, the Principal Investigator must inform the IRB and all other applicable regulatory agencies of such action immediately.

Though not yet required, the CPC should be informed about any protocol amendments that potentially affect research design or data analysis (i.e., amendments affecting subject population, inclusion/exclusion criteria, agent administration, etc.).

## **12.7 Records Retention**

The Principal Investigator will maintain study-related records at least six years after study completion.

## **12.8 Conflict of Interest**

The Principal Investigator and Sub-Investigators must comply with applicable federal, state, and local regulations regarding reporting and disclosure of conflict of interest. Conflicts of interest may arise from situations in which financial or other personal considerations have the potential to compromise or bias professional judgment and objectivity. Conflicts of interest include but are not limited to royalty or consulting fees, speaking honoraria, advisory board appointments, publicly-traded or privately-held equities, stock options, intellectual property, and gifts.

The Duke University School of Medicine's Research Integrity Office (RIO) reviews and manages research-related conflicts of interest. The Principal Investigator and Sub-Investigators must report conflicts of interest annually and within 10 days of a change in status, and when applicable, must have a documented management plan that is developed in conjunction with the Duke RIO and approved by the IRB/IEC.

## 13 APPENDICES

### Appendix A Performance Status Criteria

ECOG Performance Status Scale		Karnofsky Performance Scale	
Grade	Descriptions	Percent	Description
0	Normal activity. Fully active, able to carry on all pre-disease performance without restriction.	100	Normal, no complaints, no evidence of disease.
		90	Able to carry on normal activity; minor signs or symptoms of disease.
1	Symptoms, but ambulatory. Restricted in physically strenuous activity, but ambulatory and able to carry out work of a light or sedentary nature (e.g., light housework, office work).	80	Normal activity with effort; some signs or symptoms of disease.
		70	Cares for self, unable to carry on normal activity or to do active work.
2	In bed <50% of the time. Ambulatory and capable of all self-care, but unable to carry out any work activities. Up and about more than 50% of waking hours.	60	Requires occasional assistance, but is able to care for most of his/her needs.
		50	Requires considerable assistance and frequent medical care.
3	In bed >50% of the time. Capable of only limited self-care, confined to bed or chair more than 50% of waking hours.	40	Disabled, requires special care and assistance.
		30	Severely disabled, hospitalization indicated. Death not imminent.
4	100% bedridden. Completely disabled. Cannot carry on any self-care. Totally confined to bed or chair.	20	Very sick, hospitalization indicated. Death not imminent.
		10	Moribund, fatal processes progressing rapidly.
5	Dead.	0	Dead.

### Appendix B    FACIT Fatigue Scale (version 4)

Below is a list of statements that other people with your illness have said are important.  
**Please circle or mark one number per line to indicate your response as it applies to the past 7 days.**

#### **PHYSICAL WELL-BEING**

		Not at all	A little bit	Some- what	Quite a bit	Very much
GP1	I have a lack of energy .....	0	1	2	3	4
GP2	I have nausea .....	0	1	2	3	4
GP3	Because of my physical condition, I have trouble meeting the needs of my family .....	0	1	2	3	4
GP4	I have pain .....	0	1	2	3	4
GP5	I am bothered by side effects of treatment .....	0	1	2	3	4
GP6	I feel ill .....	0	1	2	3	4
GP7	I am forced to spend time in bed .....	0	1	2	3	4

#### **SOCIAL/FAMILY WELL-BEING**

		Not at all	A little bit	Some- what	Quite a bit	Very much
GS1	I feel close to my friends .....	0	1	2	3	4

GS2	I get emotional support from my family	0	1	2	3	4
	.....					
GS3	I get support from my friends	0	1	2	3	4
	.....					
GS4	My family has accepted my illness	0	1	2	3	4
	.....					
GS5	I am satisfied with family communication about my illness	0	1	2	3	4
	.....					
GS6	I feel close to my partner (or the person who is my main support)	0	1	2	3	4
	.....					
Q1	Regardless of your current level of sexual activity, please answer the following question. If you prefer not to answer it, please mark this box  and go to the next section.					
GS7	I am satisfied with my sex life	0	1	2	3	4

**Please circle or mark one number per line to indicate your response as it applies to the past 7 days.**

EMOTIONAL WELL-BEING		Not at all	A little bit	Some-what	Quite a bit	Very much
GE1	I feel sad	0	1	2	3	4
	.....					
GE2	I am satisfied with how I am coping with my illness	0	1	2	3	4
	.....					
GE3	I am losing hope in the fight against my illness	0	1	2	3	4
	.....					

GE4	I feel nervous	0	1	2	3	4
GES	I worry about dying	0	1	2	3	4
GE6	I worry that my condition will get worse	0	1	2	3	4

**FUNCTIONAL WELL-BEING**

Not at all	A little bit	Some-what	Quite a bit	Very much
------------	--------------	-----------	-------------	-----------

GF1	I am able to work (include work at home)	0	1	2	3	4
GF2	My work (include work at home) is fulfilling	0	1	2	3	4
GF3	I am able to enjoy life	0	1	2	3	4
GF4	I have accepted my illness	0	1	2	3	4
GF5	I am sleeping well	0	1	2	3	4
GF6	I am enjoying the things I usually do for fun	0	1	2	3	4
GF7	I am content with the quality of my life right now	0	1	2	3	4

**Please circle or mark one number per line to indicate your response as it applies to the past 7 days.**

ADDITIONAL CONCERNS		Not at all	A little bit	Some- what	Quite a bit	Very much
HI7	I feel fatigued	0	1	2	3	4
HI12	I feel weak all over	0	1	2	3	4
An1	I feel listless ("washed out")	0	1	2	3	4
An2	I feel tired	0	1	2	3	4
An3	I have trouble starting things because I am tired	0	1	2	3	4
An4	I have trouble finishing things because I am tired	0	1	2	3	4
An5	I have energy	0	1	2	3	4
An7	I am able to do my usual activities	0	1	2	3	4
An8	I need to sleep during the day	0	1	2	3	4

An12	I am too tired to eat	0	1	2	3	4
	.....					
An14	I need help doing my usual activities	0	1	2	3	4
	.....					
An15	I am frustrated by being too tired to do the things I want to do	0	1	2	3	4
	.....					
An16	I have to limit my social activity because I am tired	0	1	2	3	4
	.....					

